4.4.2 Analysis of Secondary Efficacy Endpoints

Log transformed levels of lactate dehydrogenase (LDH) at Day 5 as a surrogate marker for organ damage (powered secondary endpoint)

Results of LDH will be converted to standard unit before any calculation if needed. Conversion of all lab values will be described in a separate document 'Conversion_3570_VX-X_2020-MM-DD'. Standardized results will be log transformed for this endpoint.

Log transformed levels of LDH will be analyzed using linear regression adjusted for baseline log levels of LDH, center and age. 95% confidence intervals will be additionally calculated.

In protocol the wording of "minimization factors" is used: Stratification factors from the randomization are used in models as covariates.

Before application of the linear regression, it will be checked if the residuals are approximately normally distributed (QQ-Plot, Shapiro Wilk test). If there are no major violations of the normal distribution the model can be applied. If there are major violations available only descriptive analyses will be displayed.

Point estimate together with standard error and two-sided 95% confidence interval as well as p-value (two-sided) will be reported.

28-day mortality (all cause death)

The percentage of patients who have died at Day 28 will be presented by treatment group.

The following cases may occur:

- Patient discharged from hospital **and** discontinued before Day 28, will be followed up by telephone interview to check whether they are alive or dead, if unclear as no telephone interview available, death is assumed (worst case) at last available date of early termination, hospitalization or hospital discharge
- No discharge from hospital, **but** early discontinuation before Day 28 will be followed up by telephone interview to check whether they are alive or dead, if unclear as no telephone interview available, death is assumed (worst case) at date of early termination
- Discharged from hospital, **but** no discontinuation before Day 28: No telephone interview, but regular entry at Day 28 about alive/death status

Chi-squared test or Fisher's exact test

Proportion of responder, i.e. those patients that died, as well as the p-value (two-sided) will be reported.

Logistic regression

The following co-factors will be included in the logistic regression:

- ❑ Arterial hypertension
- ❑ Diabetes

- ❑ Coronary artery disease
- ❑ Age (<65 years vs. >=65 years)
- ❑ Center

The odds ratio along with its associated 95% confidence intervals will be reported.

Ventilator-free days (VFD) (up to 28 days or hospital discharge)

VFD will be calculated as follows:

$VFD = \text{maximum}((\text{Duration in the study [days]} - \text{Duration of ventilation [days]}); 0)$

i.e. if the duration of ventilation is greater than the duration in the study, VFD is set to 0.

Duration in the study [days] = Date of study completion/ discontinuation - Date of randomization + 1.

Patients who died before or on Day 28 will be censored at the day before death (Date of death - 1).

Duration of ventilation [days] = Sum of days with all required ventilations.

If ventilation started before randomization, the duration will be counted from the date of randomization. If ventilation started and/or ended after study completion/ discontinuation, the duration will be counted until date of study completion/ discontinuation.

If ventilation is ongoing and/or no stop date is available, the duration will be calculated until date of study completion/ discontinuation or date of death respectively.

VFD will be analyzed for both all patients as well as for the subgroup of patients who were alive at Day 28 or hospital discharge/early termination. For the analysis of all patients separate analyses will be conducted for patients who died: a) VFD will be set to 0, b) the observed VFD until death will be considered.

Summary tables will be generated by treatment group.

VFD will be compared using Wilcoxon rank sum test at a significance level of 5% (two-sided) and p-value (two-sided) will be reported.

In addition, bootstrap methods will be applied to calculate 95% confidence intervals and two-sided p-values for the difference in means between treatment groups.

Proportion of responders, defined as >= 2 improvement in WHO's 11-Point Score system at Day 7, 10, 14 and 28

Patients who will be not assessed from any cause (e.g. discharge from hospital, early termination, death or in-home visit) will be considered as non-responder.

Chi-squared test or Fisher's exact test

Proportion of responder, i.e. those patients that have >= 2 improvement in WHO's 11-Point Score system, as well as the p-value (two-sided) will be reported for Day 7, 10, 14 and 28.

Logistic regression

The following co-factors will be included in the logistic regression:

- ❑ Arterial hypertension
- ❑ Diabetes
- ❑ Coronary artery disease

- Age (<65 years vs. ≥65 years)
- Center

Separate models will be calculated for Day 7, 10, 14 and 28.

The odds ratio along with its associated 95% confidence intervals will be reported.

Time to death (all causes)

Time to death [days] = Date of death - Date of randomization.

Patients who will be alive at Day 28, or who will be discharged from hospital/early terminated before Day 28 will be censored at discharge/early termination if they cannot be reached at or after Day 28 by means of a telephone interview. Patients who will be reached at or after Day 28 by means of a telephone interview will be censored at the date of telephone contact if they are alive.

The following cases may occur:

- Patient discharged from hospital **and** discontinued before Day 28, will be followed up by telephone interview to check whether they are alive or dead, if unclear as no telephone interview available, death is assumed (worst case) at last available date of early termination, hospitalization or hospital discharge
- No discharge from hospital, **but** early discontinuation before Day 28 will be followed up by telephone interview to check whether they are alive or dead, if unclear as no telephone interview available, death is assumed (worst case) at date of early termination
- Discharged from hospital, **but** no discontinuation before Day 28: No telephone interview, but regular entry at Day 28 about alive/death status

Time to death (all causes) will be analyzed using Kaplan-Meier estimates and plots, log-rank test, and Cox proportional hazards model (adjusted for center and age to derive hazard ratios and corresponding 95% confidence intervals).

Kaplan-Meier estimates and Log-rank test

Kaplan-Meier table (product-limit “survival” estimates with 95%-CI, Standard error, Number of patient with event, Number of patient at risk) for Time to death [days], Kaplan-Meier Summaries of Event/Censoring (Number of patient with event, Number of patient censored, Total number of patients), Quartile Estimates (Median Time to Event, 1st Quartile, 3rd Quartile, 95%-CI) and Kaplan-Meier table (“survival” estimates with 95%-CI) for Timepoint (28 days). Time to death [days] will be displayed by a Kaplan-Meier-curve. Treatments groups will be compared with Log-rank test.

Cox proportional hazards model

The hazards ratio along with its associated 95% confidence intervals as well as parameter estimate and p-value (two-sided) will be reported.

Proportion of patients with any use of invasive mechanical ventilation (up to 28 days or hospital discharge)

Requirement and type of ventilation will be presented using frequency tables.

Chi-squared test or Fisher’s exact test

Proportion of responder, i.e. those patients that having an invasive mechanical ventilation (up to 28 days or hospital discharge), as well as the p-value (two-sided) will be reported.

Logistic regression

The following co-factors will be included in the logistic regression:

- Arterial hypertension
- Diabetes
- Coronary artery disease
- Age (<65 years vs. >=65 years)
- Center

The odds ratio along with its associated 95% confidence intervals will be reported.

Time to first use of invasive mechanical ventilation (up to 28 days or hospital discharge)

Time to first use of invasive mechanical ventilation [days] = Start date of first ventilation - Date of randomization.

If ventilation started before randomization, the time to first use will be set to 0 (minimal possible duration).

Patients without documented invasive mechanical ventilation who completed the study or was early terminated or discharged from hospital before Day 28 will be censored at the date of study completion, discontinuation or discharge from hospital respectively.

Time to first use of invasive mechanical ventilation (up to 28 days or hospital discharge) will be analyzed using Kaplan-Meier estimates and plots, log-rank test, and Cox proportional hazards model (adjusted for center and age to derive hazard ratios and corresponding 95% confidence intervals).

Kaplan-Meier estimates and Log-rank test

Kaplan-Meier table (product-limit “survival” estimates with 95%-CI, Standard error, Number of patient with event, Number of patient at risk) for Time to first use of invasive mechanical ventilation [days], Kaplan-Meier Summaries of Event/Censoring (Number of patient with event, Number of patient censored, Total number of patients), Quartile Estimates (Median Time to Event, 1st Quartile, 3rd Quartile, 95%-CI) and Kaplan-Meier table (“survival” estimates with 95%-CI) for Timepoint (28 days). Time to first use of invasive mechanical ventilation [days] will be displayed by a Kaplan-Meier-curve. Treatments groups will be compared with Log-rank test.

Cox proportional hazards model

The hazards ratio along with its associated 95% confidence intervals as well as parameter estimate and p-value (two-sided) will be reported.

Absolute values and absolute change in PaO2/FiO2 ratio over time

The PaO2/FiO2 ratio = PaO2 [mmHg] / FiO2

This will be evaluated on each visit for ventilated patients only. If entries are not changed compared to previous entries, no entry will be done within the eCRF.

If ventilation is ongoing and/or no stop date is available, the PaO2/FiO2 ratio will be considered until date of study completion/ discontinuation or date of death respectively.

Baseline is defined as first observation of PaO2/FiO2 ratio (individual start value). Basic statistics for the PaO2/FiO2 ratio for both the absolute values and the absolute change from baseline will be tabulated by day of ventilation. Daily means will be used when more than one assessment is available per day.

Absolute values and absolute change in notified sequential organ failure assessment score (mSOFA score) over time

The mSOFA score was introduced with protocol version 5.0 and is available for patients who are included with protocol version 5.0 and higher. For patients who are included with previous protocol versions (protocol version 4.0 and lower), mSOFA score is available from the time when protocol is in effect at the centers.

Basic statistics for the mSOFA score for both the absolute values and the absolute change from baseline will be tabulated by visit.

SOFA score (protocol version 4.0 and lower) will be listed only.

Time to a 2-point decrease in WHO's 11-Point Score system

Time to 2-point decrease [days] = Assessment date of first ≥ 2 improvement - Date of randomization.

Patients without documented 2-point decrease who completed the study or was early terminated or discharged from hospital before Day 28 will be censored at the date of last WHO assessment available.

Time to 2-point decrease will be analyzed using Kaplan-Meier estimates and plots, log-rank test, and Cox proportional hazards model (adjusted for center and age to derive hazard ratios and corresponding 95% confidence intervals).

Kaplan-Meier estimates and Log-rank test

Kaplan-Meier table (product-limit "survival" estimates with 95%-CI, Standard error, Number of patient with event, Number of patient at risk) for Time to 2-point decrease [days], Kaplan-Meier Summaries of Event/Censoring (Number of patient with event, Number of patient censored, Total number of patients), Quartile Estimates (Median Time to Event, 1st Quartile, 3rd Quartile, 95%-CI) and Kaplan-Meier table ("survival" estimates with 95%-CI) for Timepoint (28 days). Time to 2-point decrease [days] will be displayed by a Kaplan-Meier-curve. Treatments groups will be compared with Log-rank test.

Cox proportional hazards model

The hazards ratio along with its associated 95% confidence intervals as well as parameter estimate and p-value (two-sided) will be reported.

Absolute values and absolute change in lymphocyte counts over time

Results of lymphocyte counts will be converted to standard unit before any calculation if needed. Conversion of all lab values will be described in a separate document.

Basic statistics for both the absolute values and the absolute change from baseline will be tabulated by visit.

Absolute values and absolute change in C-reactive protein levels over time

Results of C-reactive protein will be converted to standard unit before any calculation if needed. Conversion of all lab values will be described in a separate document.

Basic statistics for both the absolute values and the absolute change from baseline will be tabulated by visit.

Absolute values and absolute change in D-dimer over time

Results of CD-dimmer will be converted to standard unit before any calculation if needed. Conversion of all lab values will be described in a separate document.

Basic statistics for both the absolute values and the absolute change from baseline will be tabulated by visit.

Absolute values and absolute change in log transformed levels of LDH over time

Results of LDH will be converted to standard unit before any calculation if needed. Conversion of all lab values will be described in a separate document. Standardized results will be log transformed for this endpoint.

Basic statistics for both the absolute values and the absolute change from baseline will be tabulated by visit.

Time to hospital discharge

Time to hospital discharge [days] will be calculated as Date discharge from hospital - Date of randomization.

The first discharge from hospital will be used for this endpoint. Patients without hospitalization or without documented hospital discharge who completed the study or was early terminated before Day 28 will be censored at the date of study completion or discontinuation respectively. Patients who have died before Day 28 will be censored at the date of death.

Time to hospital discharge will be analyzed using Kaplan-Meier estimates and plots, log-rank test, and Cox proportional hazards model (adjusted for center and age to derive hazard ratios and corresponding 95% confidence intervals).

Kaplan-Meier estimates and Log-rank test

Kaplan-Meier table (product-limit “survival” estimates with 95%-CI, Standard error, Number of patient with event, Number of patient at risk) for Time to hospital discharge [days], Kaplan-Meier Summaries of Event/Censoring (Number of patient with event, Number of patient censored, Total number of patients), Quartile Estimates (Median Time to Event, 1st Quartile, 3rd Quartile, 95%-CI) and Kaplan-Meier table (“survival” estimates with 95%-CI) for Timepoint (28 days). Time to hospital discharge [days] will be displayed by a Kaplan-Meier-curve. Treatments groups will be compared with Log-rank test.

Cox proportional hazards model

The hazards ratio along with its associated 95% confidence intervals as well as parameter estimate and p-value (two-sided) will be reported.

Hospitalization data will be listed additionally.

Change in viral RNA over time

Basic statistics for both the absolute values and the absolute change from baseline will be tabulated by visit.

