8 INVESTIGATIONAL PLAN

8.1 Overall Study Design and Plan-Description

The clinical trial is designed as a prospective, multi-centre, double-blind, randomized, placebo-controlled, interventional trial to assess clinical safety, tolerability, and efficacy of APN01 on top of best standard of care (SOC) in patients with severe COVID-19 and to evaluate if treatment with APN01 on top of SOC is superior to placebo (NaCl 0.9%) on top of SOC.

SOC treatment (such as Concomitant medication, remdesivir (if approved and available) and ventilation techniques) will be documented in the eCRF and considered for evaluation for study data. SOC treatment follows the national guidelines (<https://www.ersnet.org/covid-19-guidelines-and-recommendations-directory>).

The study will comprise two treatment groups as follows:

- Group A (active): APN01 (5 mg/ml, 4 ml/vial)
- Group B (placebo control): sterile, 0.9% sodium chloride

Eligible patients are centrally allocated using a dynamic randomization (1:1) to Group A or B to receive the treatment or placebo. Dynamic randomization factors will be age in years (continuous) and center. The entire study team will be blinded except for an unblinded pharmacist or an unblinded study team member (including team members involved in the IMP preparation, unblinded statisticians and DSMB members involved in DSMB, unblinded data managers involved in generation and the upload of treatment listings to eCRF). . Randomization will be carried out centrally using the electronic case report form (eCRF).

After screening at day -1 and randomization at day -1 or 1, the patients will be treated with APN01 or Placebo intravenously twice daily (BID) every 12 hours (\pm 1 hour) over 3 to 30 minutes in the morning and the evening until day 7. Preparation of APN01 (0.4mg/kg BID for seven calendar days) and placebo (normal saline) will be carried out according to the Pharmacy Manual. The IMP will be administered in a double-blind manner (investigators, study team and patients will be blinded to the treatment administered).

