Eligible patients will be centrally allocated using a dynamic randomization (1:1) at baseline (day 1) to Group A or B to receive the treatment or placebo. Dynamic randomization factors will be age in years (<65 years vs. ≥65 years), presence of at least one relevant co-morbid condition (hypertension, diabetes, coronary artery disease) for study protocol versions prior version 6.0 and center.

After screening at day -1 and randomization at day -1 or day 1, patients will be treated with APN01 or placebo intravenously twice daily (BID) every 12 hours (± 1 hour) over 3 to 30 minutes in the morning and in the evening until day 7 (14 doses). If a patient will be discharged from hospital before day 7 treatment can be stopped at day of discharge.

Periods and duration

The study will consist of three periods: screening (day -1), treatment period (day 1 to day 7) and follow-up period (day 10, day 14 and day 28). Study duration is up to 29 days per patient. Total study duration is up to 5 months, with 2-4 months recruitment period per country.

Number of patients planned

The planned sample size is 200 treated patients. Approximately 40 sites in Europe, Russia and US are planned, hence for a 1:1 (APN01:Placebo) randomization scheme. 186 patients (93 per group) will yield 80% power to detect a 20% absolute risk reduction in the primary composite endpoint, from 50% in the placebo group to 30% in the APN01 group at a two-sided alpha of 0.05. To consider patients who will be randomized but not treated a total of 200 patients (100 per group) will be enrolled.

DSMB Meetings

The regular DSMB will be performed after randomization of 8-10, 20, 50, 100 (if necessary), and 150 (if necessary) patients. Furthermore an ad hoc meeting of the DSMB may be called at any time by the DSMB Chair, coordinating investigator, medical monitor or sponsor imminent for any significant reason.

Study objectives

The primary study objective is to assess clinical efficacy of APN01 using a composite outcome of all cause-death or need of invasive mechanical ventilation up to 28 days.

The secondary study objectives are to assess efficacy of APN01 using log transformed levels of Lactate dehydrogenase (LDH) as a surrogate marker for organ damage, to evaluate the safety of APN01 in patients with severe COVID-19 and to monitor other biomarker changes (e.g. IL-6, Ang II) in patient with severe COVID-19 treated with APN01.

2 Efficacy and Safety Endpoints

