Page # of #

<Subtitle for description of contents - if applicable>

<Analysis set>

The numbering NNN of the tables/listings/graphs will be stated in the detailed description (Appendix A).

Following footnote will be used for all generated tables, listings, and graphs:

Date: <Actual date(ddmmmyyyy)>

Program: <Name of program>

All tables, listings, and graphs will be generated in A4 paper format.

The statistical evaluation will be performed using SAS version 9.4 or higher.

5 Changes from Protocol

In the following any changes on statistical aspects as described in the protocol are given:

- Wording of WHO's Proposed Core Outcome Measure Set for Clinical Studies of COVID-19 Infection for consistence (secondary endpoint):
 - Protocol: Time to a 2-point decrease in WHO scoring schema
 - SAP: Time to a to a 2-point decrease in WHO's 11-Point Score system
- Covariables used in statistical models and dynamic randomization
 - Protocol: Age as continuous variable
 - SAP: Age as dichotomous variable (<65 years vs. >= 65 years)

6 Signatures

Statistician:	
[name] FGK Clinical Research GmbH [name] [name] Germany	
11 Jan 2021 Date (ddmmmyyyy)	SN [Signature] Signature

Sponsor:	
[name] APEIRON Biologics AG [name]	
11 Jan 2021 Date (ddmmmyyyy)	[Signature] Signature

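### The LDH regression and the four Cox models leave out comorbidity, a randomisation factor before protocol version 6.0, although the SAP says randomisation factors are model covariates

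*SAP*

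**What the plan says.** **The rule.** Under the LDH endpoint in SAP 4.4.2, the protocol's term for minimisation factors is explained as follows: "Stratification factors from the randomization are used in models as covariates". Protocol 8.7.1.2.5 uses that term for both the LDH regression and the Cox model for time to death.

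**The factors.** SAP section 1 (Methodology) names three: age (under 65 versus 65 or older), center, and "presence of at least one relevant co-morbid condition (hypertension, diabetes, coronary artery disease) for study protocol versions prior version 6.0". The protocol's summary of changes dates the removal of comorbidity to the amendment from version 5.0 to 6.0, 08 Jun 2020. Protocol 8.1 in the current version 7.0 says: "Dynamic randomization factors will be age in years (continuous) and center".

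**The models.**
- LDH at Day 5: "Log transformed levels of LDH will be analyzed using linear regression adjusted for baseline log levels of LDH, center and age".
- Time to death, to first invasive ventilation, to 2-point WHO decrease and to discharge: each Cox model is "adjusted for center and age to derive hazard ratios and corresponding 95% confidence intervals".
- All logistic models (primary composite, 28-day mortality, WHO responders, invasive ventilation): hypertension, diabetes and coronary artery disease as three terms, plus age cut at 65 and center.

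**Declared changes.** SAP section 5 has an entry on model covariates and dynamic randomisation. It covers only age, changed from continuous to a cut at 65. Comorbidity is not mentioned.

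**The concern.** The SAP states a rule and a list of factors, and five models then leave one listed factor out without a reason. As a result, 28-day mortality is adjusted for comorbidity in its logistic model, while time to death, which uses the same deaths, is not adjusted for it in its Cox model.

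The documents themselves treat comorbidity as prognostic. Protocol 6.1 cites a UK hospital cohort in which comorbidities went with higher mortality, and Protocol 6.7 cites a cohort in which they went with intensive care admission. If a prognostic factor has been balanced by design and is then ignored in a linear model, the standard error comes out too large and the test is conservative. In a Cox model, leaving out a prognostic covariate pulls the hazard ratio toward 1 and loses power. What is at stake is precision on secondary endpoints, including LDH, which the SAP labels as powered.

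**Working it through.** **1. The plan's own figure.** The only design calculation with stated inputs is for the primary endpoint: 50% versus 30%, two-sided 0.05, 80% power, chi-squared test.

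n per group = [1.960·√(2·0.4·0.6) + 0.8416·√(0.5·0.5 + 0.3·0.7)]² / 0.2² = (1.3579 + 0.5708)² / 0.04 = 93.0

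This gives 93 per group and 186 in total, as stated. It does not depend on covariates in the secondary models. No inputs are given for LDH, so a gain in LDH precision cannot be turned into a change in planned power.

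**2. Factors against models.**

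| Factor listed in SAP section 1 | LDH regression | Four Cox models | Logistic models |
|---|---|---|---|
| Center | yes | yes | yes |
| Age | yes | yes | yes |
| Comorbidity (before version 6.0) | **no** | **no** | yes, as three conditions |

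**3. Size in the LDH model, closed form.** Assume comorbidity explains a share R² of the variance left after the planned covariates. The documents give no value, so a range is shown.
- Standard error ratio = 1/√(1−R²)
- Equivalent extra patients = 200/(1−R²) − 200
- Size of a nominal 5% test that ignores the factor = 2·[1−Φ(1.96/√(1−R²))]. This holds only if every patient was balanced on comorbidity, so it is an extreme case here.

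| R² | SE wider by | Extra patients | Size (extreme case) |
|---|---|---|---|
| 1% | 0.5% | 2.0 | 4.9% |
| 5% | 2.6% | 10.5 | 4.4% |
| 10% | 5.4% | 22.2 | 3.9% |

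**4. Size in a linear model, simulated.** Assumed inputs: 200 patients, 40 centers, comorbidity in 50%, residual SD 0.8, age effect 0.3 per SD, comorbidity effect 0.3 or 0.6, no treatment effect, 2000 runs per row. Allocation is by minimisation on center and age, with comorbidity added for the first 10%, 50% or 100% of patients. Both models include a baseline covariate, center and age cut at 65.

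| Share balanced | Effect | SE without | SE with | Ratio | Rejection without | Rejection with |
|---|---|---|---|---|---|---|
| 10% | 0.3 | 0.1232 | 0.1216 | 1.013 | 0.0415 | 0.0420 |
| 10% | 0.6 | 0.1291 | 0.1217 | 1.061 | 0.0495 | 0.0510 |
| 50% | 0.3 | 0.1236 | 0.1218 | 1.015 | 0.0465 | 0.0450 |
| 50% | 0.6 | 0.1296 | 0.1219 | 1.063 | 0.0445 | 0.0485 |
| 100% | 0.3 | 0.1252 | 0.1233 | 1.015 | 0.0455 | 0.0500 |
| 100% | 0.6 | 0.1313 | 0.1234 | 1.064 | 0.0340 | 0.0440 |

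These rows balance age as continuous. With age balanced on the cut (50%, effect 0.6), the ratio is 0.1312/0.1234 = 1.063 and rejection is 0.0425 without and 0.0495 with the term.

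The Monte Carlo standard error at 5% is √(0.05·0.95/2000) = 0.005. Only the 0.034 is clearly below nominal, and nothing is clearly above it. The gain in standard error hardly depends on how many patients were balanced. The conservatism shows clearly only when all patients were balanced and the effect is strong.

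**5. Cox models.** The formulas in step 3 are linear-model results and do not carry over. Only the direction of the effect is claimed.

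**The case against.** The strongest defence is that the SAP is based on protocol version 7.0, whose only factors are age and center. The rule comes directly after a model that lists center and age, so it may be meant to cover only the factors that apply to every patient. The documents do not say how many patients were randomised before version 6.0, and the number may be small. Secondary endpoints are tested in an exploratory manner (Protocol 8.7.1.2.5).

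Much of this stands, and it limits the weight of the point. It does not remove it. The SAP itself lists comorbidity as a randomisation factor, section 5 gives no reason for leaving it out, and the logistic models use it. The precision gain also does not need the patients to have been balanced on comorbidity.

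A reader might infer three stronger things that the documents do not support:
- **That cutting age at 65 also breaks the rule.** It does not. SAP section 1 gives the randomisation factor in that cut form, and section 5 declares the change. The cut costs a little precision (about 3% in the standard error on the inputs above), which makes continuous age a preference and not a correction.
- **That the omission favours the drug or inflates type I error.** Any effect is in the conservative direction.
- **That the primary result is affected.** The primary test is an unadjusted chi-squared test, and its supporting logistic model already contains the three conditions.

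**Conclusion.** The SAP's rule and its own list of factors do not match five of its models, and the omission is not declared. The effect is small: about 1% to 6% on the LDH standard error, resting on assumed prognostic strength and prevalence, and an unquantified loss of power with some attenuation of the hazard ratio in the Cox models. It is confined to exploratory secondary endpoints. It is still worth correcting, because the fix is nearly free.

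A separate mismatch about age needs an answer. Protocol 8.1 and the synopsis say age entered the randomisation as a continuous variable; SAP sections 1 and 5 say it was cut at 65. An SAP signed on 11 Jan 2021 can change an analysis covariate, but it cannot change how patients had already been allocated. The documents do not settle which form the algorithm used.

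**What to change.** 1. In SAP 4.4.2, add a term for at least one relevant comorbidity (yes/no) to the LDH regression and to the four Cox models, for all patients whatever protocol version they entered under. The cost is one degree of freedom per model and a line of text. The data are already needed: SAP 4.2 tabulates this variable, and the logistic models use its components.
2. If the sponsor prefers to leave it out, say so in SAP section 5 with the reason, and report how many patients were randomised before version 6.0.
3. State in the SAP which form of age the randomisation algorithm actually used, and correct the document that is wrong. Keep the cut at 65 in the main models if that was the factor used, with continuous age at most as a sensitivity analysis.
4. Make the change before unblinding. If unblinding has already taken place, report the models with the comorbidity term as sensitivity analyses beside the planned ones.
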